### **I. Hypotheses and Specific Aims:**

#### Hypothesis:

Dalbavancin maintains adequate plasma and peritoneal fluid concentrations for 2 weeks after a single 1500 mg dose when administered intravenously or intraperitoneally, making it a viable and convenient option for treating peritoneal dialysis patients with peritonitis

#### Specific Aims:

1. Determine dalbavancin plasma pharmacokinetics in peritoneal dialysis patients after intravenous and intraperitoneal administration
2. Determine dalbavancin peritoneal fluid pharmacokinetics in peritoneal dialysis patients after intravenous and intraperitoneal administration
3. Evaluate patients for any adverse effects potentially associated with intraperitoneal administration of dalbavancin

### **II. Background and Significance:**

Every year in the United States approximately 110,000-115,000 patients are newly diagnosed with end-stage renal disease (ESRD) and begin treatment with renal replacement therapy. Nearly 10,000 of these patients are started on peritoneal dialysis (PD). The use of home dialysis has increased significantly (35% increase) in the last decade, with 95% of home dialysis patients undergoing PD. Infectious peritonitis is a leading major morbidity associated with PD, and it accounts for approximately 18% of infection-related mortality in PD patients. Severe or prolonged peritonitis can lead to peritoneal membrane failure, ultimately causing technical failure of PD and requiring transition to traditional hemodialysis methodologies. Rapid and effective treatment of peritonitis is required to reduce inflammation and preserve peritoneal membrane function. The current standard of care involves empiric antibiotics covering gram positive organisms as staphylococcus aureus, coagulase negative staphylococcus and enterococcus are common infecting pathogens. Vancomycin is commonly employed at most institutions as there is a risk of MRSA infections in this patient population. Addition of a second drug for gram negative bacteria coverage is recommended until culture and sensitivity results are available. Intravenous or intraperitoneal administration of antibiotics can be utilized; however, guidelines recommend the intraperitoneal administration of antibiotics with a dwell time of at least 6 hours because it provides instant, high, and sustained concentrations of the antibiotic in the peritoneal fluid. Although vancomycin covers the majority of gram positive organisms that cause peritonitis, its use can be cumbersome in PD patients. Plasma vancomycin drug concentration monitoring must occur to evaluate for vancomycin accumulation. Additionally, vancomycin must be re-administered every 3-5 days in order to maintain steady-state trough concentrations around 15 mcg/ml. Similarly to vancomycin, dalbavancin interferes with cell wall synthesis. This is done through binding of the D-alanyl-D-alanine terminus of the cell wall peptidoglycan. Dalbavancin has been shown to rapidly reach therapeutic systemic concentrations and to have an extended half-life of ~8.5 days. Dalbavancin has been shown safe and effective with a treatment doses of 1500 mg once or 1000 mg followed by a 500 mg dose on day 7. Dalbavancin pharmacokinetics were evaluated in patients who had hepatic or renal impairment. This study showed compared to healthy subjects dalbavancin exposure was not increased in mild renal impairment, exposure was ~50% higher in moderate renal impairment, 100% higher in severe renal impairment, and not significantly different in end stage renal disease

patients undergoing dialysis. Based on this data only patients with severe renal dysfunction, <30 mL/min, and not on hemodialysis should have their dalbavancin dose reduced.

We believe that dalbavancin offers a unique option for PD patients with peritonitis, because it has excellent gram positive bacteria coverage, is administered in a single dose option, does not require dose adjustment in renal dysfunction on dialysis, and there is no need for routine plasma concentration monitoring. For these reasons, we intend to study the pharmacokinetics of dalbavancin when administered intravenously and intraperitoneally in PD patients.

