#### C. Study Design and Research Methods

This study is an open label, cross-over study, evaluating the plasma and peritoneal fluid pharmacokinetics of dalbavancin after either intravenous or intraperitoneal administration. The

patients will be randomly assigned to receive dalbavancin either intravenously or intraperitoneally on study visit 1. The patients will receive the alternate administration technique following the washout period at visit 4. Patients will be administered dalbavancin either intravenously or intraperitoneally on study day 0. Pharmacokinetic analysis will be conducted on days 0, 7, and 14. Following the wash out period of 45 days or greater, the same 10 patients will cross-over and then be administered dalbavancin via the alternate administration technique received in visit 1 on study day 0. Pharmacokinetic analysis will be conducted again on days 0, 7, and 14. (see Appendix 1)

*Sample Size:*

Ten (n=10) patients will be evaluated in this pharmacokinetic evaluation. Since this is a descriptive pharmacokinetic study a sample size calculation was not performed

*Plasma and peritoneal fluid sampling:*

Dalbavancin will be administered on study day 0. On the intravenous administration day dalbavancin will be administered as a 30-minute IV infusion. On the intraperitoneal administration day, dalbavancin will be administered in the peritoneal dialysis fluid with a 6 hour dwell time. On day 0, patients will undergo plasma and peritoneal fluid pharmacokinetic sampling for determination of dalbavancin concentrations at time zero, 1 hour, 2 hours, 3 hours, 4 hours, 6 hours, at time of volume exchange. Patients will be given a specimen collection cup and asked to collect ~30 ml of peritoneal dialysate following scheduled nocturnal dwell approximately 24 hours following the administration of dalbavancin administration. Patients will report for a single PK measurement on study days 7 and 14. (18 total plasma and 18 total peritoneal fluid samples per patient). Blood samples will be drawn from a peripherally inserted intravenous catheter. Peritoneal fluid samples will be drawn from the already placed peritoneal dialysis catheter. Blood samples will be immediately centrifuged at 3000g and plasma and peritoneal fluid samples will be stored at -80°C until analysis.

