**D. Description, Risks and Justification of Procedures and Data Collection Tools:**

**Enrollment and Screening:** Study subjects will be contacted an enrolled through [name] clinic. Initial contact will be made by phone prior to a clinic appointment to discuss initial interest of the patient. Further information and enrollment will take place at a clinic visit or time of the patients choosing. Enrollment will take place in a private room at [name] clinic. Initial baseline and demographic information will be gathered for enrolled patients at the time of enrollment. Safety labs (comprehensive metabolic panel and urine pregnancy test for women of childbearing potential) will be drawn or performed at [name] clinic and will coincide with a scheduled clinic visit closest to study protocol initiation. The comprehensive metabolic panel will be drawn to evaluate Child-Pugh score if there is no comprehensive metabolic panel within the medical record within 30 days of protocol initiation.

**Visit 1 and 4:** (~8 hours): On visits 1 and 4 the patients will undergo intensive PK sampling. Inclusion and exclusion criteria will be reviewed with the patient at each visit prior to initiation of the protocol. Subjects will be admitted to the CTRC in the morning and a "saline-lock" will be placed. The dalbavancin preparations will be prepared and managed by [name] or [name] who are both clinical pharmacists with training in sterile drug preparation. The dalbavancin 1500 mg will either be administered, by CTRC nursing staff, intravenously (as randomly assigned) or into the intraperitoneal space (as randomly assigned) using the patient's existing peritoneal dialysis catheter with the patients currently prescribed dialysate. Following the blood and peritoneal fluid collection at the second dialysis volume exchange, the subjects will be discharged and asked to return at a scheduled time on day 7. Patients will also be given a specimen collection up with instructions to collect approximately 30 ml of peritoneal dialysate following their evening nocturnal dwell. The collected dialysate will be returned to the investigators.

**Visit 2, 3, 5, and 6:** (~60 minutes): A "saline-lock" will be placed and a single blood and peritoneal fluid sample will be collected at each of these visits. All blood and peritoneal fluid draws will be

completed at the outpatient CTTC. The patient will be discharged and follow up visits will be scheduled for day 14 or next intensive PK sampling visit.

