**Washout:** During the 45 day or greater washout portion of this study the patients will not be asked to come in for any visits. This timeframe, which is greater than 5 half-lives of dalbavancin, is to ensure that all of the medication (dalbavancin) has left the patients' system before administering another dose of the medication.

**Laboratory tests:** The laboratory tests to be performed as part of this study include pregnancy testing to confirm eligibility and comprehensive metabolic panels if one is not documented within 30 days prior to the initiation of protocol to determine Child-Pugh score. These will be done at an initial screening visit if required to coincide with clinic appointment before visit 1.

**Pharmacokinetic Assessments:** 4 mL of blood will be collected in a purple top (EDTA) tube and 4 mL of peritoneal fluid in a urine collection cup at pre-dose, and 1, 2, 3, 4, 6, dialysis volume exchange. Blood and peritoneal fluid will be placed in an ice bath to chill until centrifuged. Plasma will be harvested within 30 minutes of each blood sample and will be stored at -80°C until assaying.

**Sample Coding and Storage:** Study samples will be coded with an indirect identifier and stored in [name] access-controlled laboratory.

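### The Background is inconsistent about whether the dose-reduction exemption covers peritoneal dialysis, and the washout rests on a half-life not shown for these patients, with no carry-over correction in the analysis

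*Combined protocol and SAP*

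**What the plan says.** **Dose rationale (Section II).** Exposure relative to healthy subjects is reported as "100% higher in severe renal impairment, and not significantly different in end stage renal disease". The sentence then specifies patients undergoing dialysis and names no modality. The following sentence concludes that "only patients with severe renal dysfunction, <30 mL/min, and not on hemodialysis should have their dalbavancin dose reduced". The next paragraph argues for studying dalbavancin in PD partly because it "does not require dose adjustment in renal dysfunction on dialysis". Section IV.D gives every patient the same dose in both periods: "The dalbavancin 1500 mg will either be administered" by one route or the other at visits 1 and 4.

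**Washout (Section IV.D).** The interval is described with the words "During the 45 day or greater washout portion of this study" and justified as one "which is greater than 5 half-lives of dalbavancin", so that no drug remains before the second dose. The only half-life in the documents is the general one in Section II, an "extended half-life of ~8.5 days". The schedule in Appendix 2 puts the washout between visit 3 (day 14) and visit 4.

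**Sampling and analysis.** In Section IV.C, "Pharmacokinetic analysis will be conducted on days 0, 7, and 14", with a time-zero sample at each intensive visit. Section IV.F calculates AUC and other parameters for each route and compares routes with a paired t-test. It gives no use for the visit 4 pre-dose concentration and has no term or correction for carry-over.

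**The concern.** PD is dialysis but not hemodialysis. Read literally, a PD patient below 30 mL/min is inside the dose-reduction group in one sentence and exempt in the next paragraph. Every trial patient is on PD, so the rationale for the stated dose should be consistent for exactly this group.

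The washout has a related gap. Its length is justified by a half-life that is not specific to PD, in a study whose aim is to measure elimination in PD. If elimination is slower than assumed, drug from period 1 is still present at visit 4. It is then counted in the concentrations and AUC of whichever route comes second. This affects the period 2 pharmacokinetic parameters, which are primary endpoints, and the paired comparison of routes.

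**Working it through.** **1. Scope of the exemption**

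| Statement in Section II | Who is exempt or unchanged | Does it settle PD? |
|---|---|---|
| Exposure by renal group | End-stage patients undergoing dialysis | Modality not stated |
| Dose-reduction sentence | Hemodialysis | PD below 30 mL/min not exempt, read literally |
| Next paragraph | Dialysis | PD exempt |

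The last two rows differ for PD, and the first does not say which modality was studied.

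**2. The plan's own washout figure**

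Inputs: half-life 8.5 days (Section II); washout at least 45 days (Section IV.D).

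45 / 8.5 = 5.29 half-lives; 5 × 8.5 = 42.5 days, which is less than 45. The stated figure is reproduced.

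**3. Residual at the second dose**

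Assuming first-order elimination, residual fraction r = 2^(−interval / half-life). Two intervals are used: 45 days, and 14 + 45 = 59 days from dose to dose if the washout starts after day 14, as Appendix 2 shows.

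The documents give exposure but no half-life by renal group. For illustration, assume volume of distribution is unchanged, so half-life rises in proportion to exposure: 8.5 × 1.5 = 12.75 days and 8.5 × 2 = 17 days.

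| Half-life | Interval | Half-lives elapsed | Residual r |
|---|---|---|---|
| 8.5 days (protocol) | 45 days | 5.29 | 2.5% |
| 8.5 days (protocol) | 59 days | 6.94 | 0.8% |
| 12.75 days (exposure +50%) | 45 days | 3.53 | 8.7% |
| 12.75 days (exposure +50%) | 59 days | 4.63 | 4.0% |
| 17 days (exposure +100%) | 45 days | 2.65 | 16.0% |
| 17 days (exposure +100%) | 59 days | 3.47 | 9.0% |

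**4. Where the 5-half-life statement stops holding**

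- 45-day interval: 45 / 5 = 9.0 days, which is 9.0 / 8.5 = 1.06, or 6% above the stated half-life.
- 59-day interval: 59 / 5 = 11.8 days, which is 11.8 / 8.5 = 1.39, or 39% above it.
- If clearance were halved, the statement would survive only if volume fell below 9.0 / 17 = 0.53 (45 days) or 11.8 / 17 = 0.69 (59 days) of its usual value.

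**5. Effect on the route comparison**

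Let A and B be the true intravenous and intraperitoneal AUC and D = A − B. Under one-compartment linear kinetics, residual r adds r times the period 1 AUC to period 2.

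- Intravenous first: observed difference = A − (B + rA) = D − rA.
- Intraperitoneal first: observed difference = (A + rB) − B = D + rB.
- Equal numbers in each order: mean = D − (r/2)(A − B) = D(1 − r/2).

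The shrinkage is therefore r/2: 16% / 2 = 8% or 9% / 2 = 4.5% at a 17-day half-life, and 2.5% / 2 = 1.3% or 0.8% / 2 = 0.4% at 8.5 days. If a share p starts intravenously, there is an extra term r(½ − p)(A + B), which does not vanish when D is zero. Section IV.C says that order is random but not that it is balanced.

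**6. How well period 1 alone can check the half-life**

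After day 0, plasma is drawn only on days 7 and 14; the 24-hour sample is dialysate only. With a 17-day half-life, the log ratio between those days is 0.693 × 7 / 17 = 0.285. If each concentration carries 10% error (assumption), its standard error is √2 × 0.10 = 0.141, so the relative error is 0.141 / 0.285, about 50%. Adding the visit 4 pre-dose value 45 days after day 14 gives a log ratio of 0.693 × 45 / 17 = 1.83 and a relative error of 0.141 / 1.83, about 8%, provided the concentration is measurable.

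**The case against.** A reader might infer that the protocol places PD patients among those with doubled exposure, and that the stated dose or the washout is therefore wrong. The documents do not support this. No sentence assigns PD patients to that group. The exposure sentence puts end-stage patients on dialysis in the unchanged group, and Section II itself introduces PD as a treatment for end-stage disease. Reaching the other reading takes a literal use of the word hemodialysis plus an assumed renal function below 30 mL/min, and the inclusion criteria set no such threshold. This part of the objection stands: the conflict is one of scope, not a stated contradiction about exposure.

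Four further points on the plan's side are fair:

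- A first pharmacokinetic study in a population has to plan its washout from prior data. Using 8.5 days is not an error, and the arithmetic is right.
- Forty-five days is a minimum, and Appendix 2 supports the longer 59-day interval, which tolerates a half-life up to 11.8 days.
- Random order limits the effect on the mean difference to about r/2, if the sequences are balanced.
- The pre-dose sample at visit 4 would already reveal carry-over.

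These points reduce the likely size but leave a gap. Random order does not stop period 2 parameters from being inflated in individual patients. A pre-dose sample that the analysis never uses reveals carry-over without removing it.

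**Conclusion.** Two limited points hold.

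First, Section II is inconsistent in scope for PD, and it must be reconciled with the dosing described for visits 1 and 4. Nothing here says which reading, or which dose, is right.

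Second, the washout claim is correct at 8.5 days but unverified for PD. Even at that half-life, the statement that no drug remains is too strong, since 2.5% (45 days) or 0.8% (59 days) is left. The 16% and 9% residuals, and the 8% and 4.5% shrinkage of the route difference, are illustrations. They rest on doubled exposure, unchanged volume, first-order one-compartment kinetics and, for the shrinkage, balanced sequences. It would go too far to say that the washout fails for these patients: no half-life, clearance or volume is given for PD or for severe impairment.

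The practical weight lies in the analysis. A possible bias in the period 2 parameters and the paired comparison is left uncorrected although the sample needed to correct it is already drawn.

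**What to change.** - **Sections II and IV.D (visits 1 and 4):** reconcile the wording by stating which exposure data are taken to apply to PD and on what basis.
- **Section IV.D (washout):** replace the statement that the drug is entirely gone with the expected residual, the half-life assumed, and the interval used (from the dose or from day 14).
- **Section IV.F:** report each patient's visit 4 pre-dose plasma and peritoneal concentrations. Before the paired comparison, correct period 2 concentrations and AUC for the decaying residual, or model both periods jointly. Treat the half-life from days 7 and 14 alone as a weak supporting check.

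The cost is protocol wording, slightly more analysis work, and some added variance from the correction. No new samples or visits are needed.

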### III. Preliminary Studies/Progress Report:

[name] follows 35-40 patients undergoing peritoneal dialysis within his clinic. Approximately 95% of the patients followed in his clinic meet inclusion and exclusion criteria.

### IV. Research Methods

#### A. Outcome Measure(s):

The primary endpoints for the study are to (1) determine dalbavancin plasma pharmacokinetics in peritoneal dialysis patients after intravenous and intraperitoneal administration and (2) determine dalbavancin peritoneal fluid pharmacokinetics in peritoneal dialysis patients after intravenous and intraperitoneal administration.

Secondary endpoint is to evaluate patients for any adverse effects potentially associated with intraperitoneal administration of dalbavancin.

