**Safety Assessments:**

All clinical and laboratory adverse events will be graded according to the Common Terminology Criteria for Adverse Events v4.0 as outlined in Appendix 3. All patient reported adverse events will be evaluated. The most common reactions seen with dalbavancin to date are nausea, vomiting, diarrhea, headache, rash, and pruritis. For patients on study protocol following both intravenous and intraperitoneal dalbavancin administration, in the event of grade 2 or higher clinical or laboratory adverse events, these will be reported to the study physician, [name] or the study safety officer [name] within 24 hours and the need for and type of follow-up care will be determined by [name] or [name] (e.g., physician evaluation, follow-up labs, discontinuation of study medication, etc). Subjects will be discontinued from study for any grade 3 or 4 adverse events associated with dalbavancin administration.

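### The secondary endpoint is harm from intraperitoneal dosing, but no effluent measure is scheduled, so peritoneal inflammation without symptoms would go unrecorded

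*Combined protocol and SAP*

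**What the plan says.** Aim 3 is "Evaluate patients for any adverse effects potentially associated with intraperitoneal administration of dalbavancin". Section IV.A carries this over as the only secondary endpoint, in these words: "Secondary endpoint is to evaluate patients for any adverse effects potentially associated with intraperitoneal administration of dalbavancin". Neither place names a measure, a time point or a comparison.

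Section IV.D deals with adverse events under its safety heading. The grading rule is "All clinical and laboratory adverse events will be graded according to the Common Terminology Criteria for Adverse Events v4.0 as outlined in Appendix 3", and on ascertainment the same paragraph says "All patient reported adverse events will be evaluated". In Appendix 3, grade 1 includes asymptomatic events and those found only by clinical or diagnostic observation. Appendix 2 has clinical adverse events assessed at visits 1 to 6.

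The laboratory tests are limited: "The laboratory tests to be performed as part of this study include pregnancy testing to confirm eligibility and comprehensive metabolic panels". The panel serves the Child-Pugh score, and Appendix 2 places both tests at the two dosing visits only.

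Peritoneal fluid is sampled pre-dose, at 1, 2, 3, 4 and 6 hours, at the volume exchange, at about 24 hours (a home-collected cup of about 30 mL), and on days 7 and 14, in each period. The day 0 samples are "4 mL of peritoneal fluid in a urine collection cup". Sections IV.C, IV.D and IV.F give the fluid one use, the dalbavancin assay, and the samples are frozen at -80°C.

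**The concern.** The intraperitoneal route differs from the intravenous one in putting the drug in direct contact with the peritoneum. Local irritation is therefore the adverse effect most specific to the route, and the effluent is where a symptomless form of it could be seen. The plan counts laboratory and asymptomatic events in principle but schedules no test that could produce one for the peritoneum.

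Section IV.G says the side effect profile may help open further uses of the drug, including peritonitis. If the adverse event table shows nothing specific to the intraperitoneal route, readers may take that as evidence of local tolerance. For effects without symptoms, the plan would have collected nothing on which to base that reading. Frozen samples cannot be counted later, so the gap has to be closed before enrolment.

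**Working it through.** The plan states no figure for this endpoint, so there is none to reproduce. The one stated detectable difference (1527 mg·hr/L) concerns the area under the curve and has no bearing here.

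**Step 1: what each part of the plan could detect.**

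| Item | Where | Could it show symptomless peritoneal inflammation? |
|---|---|---|
| Patient-reported events | IV.D Safety Assessments | No, by definition |
| Clinical adverse event assessment, visits 1–6 | Appendix 2 | Only if someone notices a sign; no effluent check is asked for |
| Metabolic panel, pregnancy test | IV.D, Appendix 2 | No; neither examines the effluent, and none is scheduled after the second dose |
| Temperature, tenderness, active peritonitis | Exclusion criteria, reviewed before dosing at visits 1 and 4 | No effluent test is named; these are entry criteria, not post-dose outcomes |
| Peritoneal fluid | IV.C, IV.D, IV.F | It could, but it goes only to drug assay |

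For a patient given the intraperitoneal dose first, the visit 4 review follows a washout of at least 45 days. For a patient given it second, no equivalent review follows the dose.

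**Step 2: how detection depends on symptoms.** The documents give neither the rate of peritoneal inflammation per intraperitoneal dose (p) nor the share of cases with symptoms (q). Both are assumed over a range. With n = 10 (section IV.C), each patient dosed once by this route:

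P(at least one case seen) = 1 − (1 − p·q)^10

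Example, p = 0.20 and q = 0.25: 1 − 0.95^10 = 0.401.

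| Assumed p | q = 100% | q = 50% | q = 25% | q = 0% |
|---|---|---|---|---|
| 5% | 40% | 22% | 12% | 0% |
| 10% | 65% | 40% | 22% | 0% |
| 20% | 89% | 65% | 40% | 0% |
| 30% | 97% | 80% | 54% | 0% |

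The q = 100% column is also the best that an effluent measure could achieve, if it caught every case.

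**Step 3: what zero cases would mean.** With 0 of 10, the exact upper 95% limit is 1 − 0.05^(1/10) = 0.259 one-sided, or 1 − 0.025^(1/10) = 0.308 two-sided. It applies only to events the study is able to detect.

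**Step 4: size of the addition.** Three time points × 2 periods = 6 counts per patient; 6 × 10 patients = 60.

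**The case against.** The strongest reply is that this is a small descriptive pharmacokinetic study whose safety follow-up is reasonable for its purpose. Much of that stands, and it rules out several stronger readings that a reader might infer.

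- *Patient report is the only safety instrument.* It is not. Clinical and laboratory events are graded, adverse events are assessed at all six visits, and on dosing days patients spend about 8 hours at the research centre, where nursing staff give the drug.
- *There is no baseline.* A clinical baseline exists through the exclusion criteria. Only an effluent baseline is missing.
- *The intravenous period is wasted as a control.* Adverse events are collected in both periods. What is absent is an effluent measure and a stated comparison.
- *The protocol itself says that mild inflammation damages the membrane.* Section II says "Severe or prolonged peritonitis can lead to peritoneal membrane failure", in a discussion of infectious peritonitis. It does not speak of transient or symptomless inflammation.
- *The trial will declare the route harmless.* Section IV.G says only that the study may identify possible side effects.

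The practical objections also have force. The samples are frozen, so a count needs fresh fluid and a second laboratory pathway. The 24-hour cup is filled at home with no stated return time or storage. Fluid at different time points reflects different dwells, and no dwell length is stated for the intravenous day.

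What survives is that the endpoint concerns harm from this route, the plan admits laboratory and asymptomatic events, and no scheduled measure could find one in the peritoneum.

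**Conclusion.** The concern holds in this limited form. It is an inexpensive improvement to the sole secondary endpoint; it is not a contradiction in the plan, and the pharmacokinetic aims are unaffected. As written, peritoneal inflammation without symptoms would be recorded only by chance.

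How much is lost depends on two quantities that the documents do not give. At an assumed 20% rate, the chance of seeing any case falls from 89% with full detection to 40% if a quarter of cases have symptoms and to nil if none do. These figures show how detection depends on symptoms. They are not evidence that such inflammation occurs or that it does lasting harm.

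The change makes the endpoint measurable but not conclusive, because 0 of 10 would still be compatible with a true rate up to about 26% (one-sided) or 31% (two-sided).

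**What to change.** Amend Pharmacokinetic Assessments, Safety Assessments and Appendix 2 as follows.

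1. Record effluent clarity at each in-clinic collection, in both periods.
2. Set aside a fresh, unfrozen aliquot at pre-dose, at the end of the 6-hour dwell (the 6-hour sample in the intravenous period) and on day 7, in both periods, for white-cell count and differential.
3. Record the dwell time of each specimen. Summarise the within-patient change from pre-dose descriptively, intraperitoneal against intravenous at the same time point, alongside reported adverse events.
4. Leave out the home-collected cup at about 24 hours unless its handling time is controlled.
5. State the limit that 0 of 10 would leave (about 26% one-sided, 31% two-sided).

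Any diagnostic threshold, use of the count for eligibility, or clinical response is for the investigators to decide.

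The cost is about 6 routine counts per patient (about 60 in total), a fresh-sample laboratory pathway and one added row in Appendix 2. No new visit or invasive procedure is needed. One limitation remains: without the 24-hour cup, a transient change between 6 hours and day 7 could still be missed.
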